##### 4.3.1.1. Severity of Adverse Event

Each AE will be graded by the Clinical Investigator as Mild, Moderate, or Severe based on the criteria specified in Section 12.1.1.1 of the protocol.

##### 4.3.1.2. Serious Adverse Event

An AE will be counted as a *serious adverse event (SAE)* if the Clinical Investigator answered "Yes" to the AE eCRF question "Is the adverse event serious?"

##### 4.3.1.3. Ocular Adverse Event

An AE will be counted as an *ocular AE* if the Clinical Investigator selected "OD", "OS", or "OU" for "Event Location" on the AE eCRF.

##### 4.3.1.4. Suspected Adverse Reaction

An AE will be counted as a suspected adverse reaction (SAR) if the Clinical Investigator answered "Related" to the AE eCRF question "Relationship to study drug".

#### 4.3.1.5. Events of Special Interest

*Events of special interest (ESI)* such as pregnancy, study medication administration error, ocular telangiectasia and bleeding events will be identified throughout the study. An event will be counted as ESI if the Clinical Investigator selected “Yes” to the AE eCRF question “Is it a protocol defined Event of Special Interest (ESI)?”

#### 4.3.2. Safety Measures

Table 5 lists the safety measures to be evaluated in this study.

#### 4.3.3. Rescue Therapy

Subjects are eligible for rescue with any anti-VEGF IVT injection during the Week 24 and Week 28 if one of the following rescue criteria is met:

- BCVA decrease of  $\geq 5$  letters from the last visit score
- CST increase from the last visit of  $\geq 50\mu\text{m}$
- The discretion of investigator

#### 4.3.4. Baseline Score

For any measure, the baseline score is the last observed measurement prior to the initial injection of study medication at the baseline visit.

#### 4.3.5. Change and Percent Change from Baseline

The *change and the percent change from baseline* in a measure at a post-baseline visit will be defined as:

- Change = score at the post-baseline visit – baseline score.
- Percent change from baseline =  $100 \times \text{change} / (\text{baseline score})$

For any measure assessed pre and post injection at visits with injection(s), only the pre-injection scores at the visit will be used to derive the change-from-baseline variable.

#### 4.3.6. Change after Injection

For any measure assessed pre and post injection, the *change after injection* is defined as:

- Change after injection = post-injection score at the visit – pre-injection score at the visit.

If multiple post-injection scores are available at the visit, then the first observation will be used to derive the change after injection.

If more than one injection were given to the subject at the same visit, change after injection in IOP will be performed for each injection.

**Table 5: Safety Measures**

Safety Measure	Note
Intraocular pressure (IOP)	
IOP will be measured by applanation tonometry and reported in millimeters of mercury (mmHg). The IOP of an eye is derived as the mean/median of two or three consecutive IOP measurements.
 
IOP will be measured before Lucentis® and 40 (±10) minutes after Lucentis® injection. If applicable, IOP will be measured again 60 (±10) minutes following Lucentis® injection. Any increase of ≥ 10 mmHg in IOP at 60 (±10) minutes post-injection will be reported as an AE.
 
The procedure will be also applied for DE-122 or Sham injection, and any post IVT injection of rescue treatment.

Slit-lamp biomicroscopy findings: lid Redness lid edema conjunctival hyperemia conjunctival edema corneal edema anterior chamber cells anterior chamber flare iris pupil lens phakic lens severity	
Slit-lamp biomicroscopy will be performed prior to Lucentis® injection and within 30 minutes after DE-122 or Sham injection, and any post IVT injection of rescue treatment.
 
Anterior Chamber Cells will be graded as 0 = No cells, 0.5 = 1-5 cells, 1 = 6-15 cells, 2 = 16-25 cells, 3 = 26-50 cells, or 4 = >50 cells.
 
Anterior Chamber Flare will be graded as 0 = None, 1 = Faint, 2 = Moderate, 3 = Marked, or 4 = Intense.
 
The iris and pupil status of an eye will be graded as either normal or abnormal.
 
The lens of an eye will be classified as phakic, aphakic, or pseudophakic.
 
The rest biomicroscopy parameters will be graded as 0 = None, 1 = Mild, 2 = Moderate, or 3 = Severe.

**Table 5: Safety Measures (Continued)**

Safety Measure	Note
Ophthalmoscopy findings: cup/disc ratio retina macula choroid vitreous	Indirect ophthalmoscopy will be performed prior to Lucentis ® injection and within 30 minutes after DE-122 or Sham injection, and any post IVT injection of rescue treatment.  Cup/disc ratio will be recorded with two decimal points (e.g., 0.80).  The retina, macula and choroid will be graded as either normal or abnormal.  Vitreous haze and opacification will be graded as: 0 = Clear Trace or 0.5+ = Trace 1+ = Few opacities, mild blurring 2+ = Significant blurring but still visible 3+ = Optic nerve visible, no vessels seen 4+ = Dense opacity obscures the optic nerve head.
Laboratory test: urinalysis hematology serum chemistry	Laboratory test results will be graded as: 1 = Normal 2 = Not Clinically Significant Abnormality 3 = Clinically Significant Abnormality 4 = No Results/Invalid Results 5 = Sample Not Collected  Refer to Section 23.4.16 of the protocol for the list of the minimum blood parameters and urine parameters.
Vital signs: systolic blood pressure diastolic blood pressure heart rate	Systolic blood pressure and diastolic blood pressure will be measured in mmHg. Heart rate will be measured by beats/minute. The average of two or three readings will be used.

**Table 5: Safety Measures (Continued)**

Safety Measure	Note
EKG	
EKG report will be reviewed by the Clinical Investigator and will be graded as:
 
1 = Normal            2 = Abnormal, Clinically Insignificant            3 = Abnormal, Potentially Clinically Insignificant            4 = Abnormal, Potentially Clinically Significant            5 = Abnormal, Potentially Exclusionary            6 = Abnormal, Clinically Significant            7 = Unable to Evaluate            8 = Unable to evaluate but measurements provided are correct

#### 4.4. Other Definitions

##### 4.4.1. Prior and Concomitant Medications

Non-study medications will be categorized into prior medications and concomitant medications. Specifically, a *prior medication* is defined as any non-study medication taken that ended prior to the treatment start date. A concomitant medication is defined as any non-study medication taken concurrently while on the study medication, i.e., the treatment period of a concomitant medication taken by a subject's needs to overlap with his/her treatment period of the study medication.

##### 4.4.2. Pharmacokinetic Measures

Table 6 lists all the PK measures to be estimated.

**Table 6: Pharmacokinetic Measures**

Pharmacokinetic Measure	Note
Area under the curve (AUC)	AUC ( $\mu\text{g/mL} \times \text{day}$ ) reflects the extent of exposure to DE-109 after injection. It equals the integral of the concentration-time curve.
$C_{max}$	$C_{max}$ denotes the peak plasma concentration of DE-109 observed after injection.
$t_{max}$	$t_{max}$ denotes the time to reach $C_{max}$ .
Elimination half-life ( $t_{1/2}$ )	$t_{1/2}$ is the time required for the concentration of DE-109 to reach half of its original value.

PK parameters will be estimated for each of the following time intervals based on plasma concentrations collected during the corresponding time interval:

- Day 1 to Week 4 visit
- Week 20 to Week 24 visit

#### **4.4.3. M-CHARTS™**

Narrow Dotted Lines with one line (Type I) and Bold Dotted Lines with one line (Type B) are used in this study to measure the severity of metamorphopsia in macular lesions. VM and HM of Type I and Type B in each eye will be examined three times. The median from the 3 measurements will be used. The VM and HM of Type I range from 0 to 2 while 0 to 2.4 for Type B. The VM and HM scores in normal eyes without metamorphopsia are 0. A large score indicates more severe metamorphopsia.

#### **4.4.4. Subretinal Hyper-Reflective Material and Retinal Pigment Epithelium Elevation**

SHRM is a morphological change seen on OCT as hyper-reflective material located external to the retina, or subretinal fluid if it is present, and internal to the RPE. SHRM will be graded as “Yes” if there is any SHRM, “No” if there is no SHRM, “Ungradable” if there is any reason it would be unable to grade because of pathology or reasons unrelated to quality of the image, and “Ungradable/Quality” if there are quality reasons that it is indeterminable that SHRM is present. An RPEE refers to RPE that is separated from Bruch’s membrane. The material external to the elevated RPE may be hypo-reflective, or have reflective material that could be pigment, blood, or CNV. The RPE may also be elevated by drusen. RPEE will be graded as “Yes” if there is any RPEE on any scan, “No” if there is no RPEE on any scan, “Ungradable” if there is any reason that it would be unable to grade because of pathology or reasons unrelated to quality of the image, and “Ungradable/Quality” if there are quality reasons that it is indeterminable that RPEE is present.

## **5. STUDY POPULATION**

### **5.1. Intention-to-Treat Population**

The *Intention-to-Treat (ITT)* Population will include all randomized subjects in the study.

### **5.2. Safety Population**

The *Safety Population* will include all subjects who received at least one injection of the study medication. It will be the study population for safety analyses performed with subjects as treated.

### **5.3. Full Analysis Set**

The *Full Analysis Set (FAS)* will include all subjects who received at least one injection of the study medication (DE-122 or Lucentis®) and provided at least one post-baseline BCVA measurement of the study eye during the study. It will be the population used for efficacy analyses performed with subjects as randomized.

### **5.4. Per-Protocol Set**

The *Per-Protocol Set (PPS)* is a subset of the FAS. It includes all FAS subjects without protocol violations that could affect the primary efficacy endpoint. It will be the analysis population for some sensitivity analyses performed with subjects as randomized.

Before the unmasking of treatment assignment, Santen's study team will review all protocol deviations, identify subjects with any protocol deviation that could impact the efficacy outcome, and determine whether or not to exclude the subject from the PPS.

### **5.5. PK Population**

The *Pharmacokinetic (PK) Population* will include all subjects who receive at least one DE-122 and have at least one quantifiable post-injection PK serum assessment. It will be the study population for PK analyses.

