The Primary Analysis is planned when all subjects complete the Week 24 visit. The Follow-up Analysis is planned at Week 32 to assess the number of anti-VEGF injections used for Rescue in addition to efficacy and safety data.

Subjects are eligible for rescue with any anti-VEGF IVT injection during the Week 24 and Week 28 if one of the following rescue criteria is met:

Rescue Criteria:

- BCVA decrease of ≥ 5 letters from the last visit score
- CST increase from the last visit of $\geq 50\mu\text{m}$
- The discretion of investigator

Figure 1: Study Schematic**7.1.1. Selection of Concentrations in the Study**

In this clinical study, two dose levels of DE-122 (2.0 mg and 4.0 mg) are being tested in subjects with wet AMD. The maximum amount of DE-122 that a subject can possibly receive is 24 mg over a 20 week period. Systemic exposure of DE-122 in this study given 6 times by IVT injection is anticipated to be significantly lower than the systemic exposure in over 500 cancer

subjects (most of whom received 10 mg/kg of TRC105 by weekly intravenous infusion). Therefore, no concerns regarding systemic toxicity are anticipated in this study.

In pre-clinical studies, the highest tested DE-122 IVT dose of 5 mg/injection in the monkey eye would correlate to 10 mg/eye in human eyes due to the difference in volume, hence the difference in vitreous volume between human and monkey (2:1 ratio) conveys a margin of safety.

In the mouse model of laser-induced CNV efficacy study, animals were given an IVT injection of DE-122 at 0.5, 1.5 and 5.0 µg/eye. DE-122 inhibited CNV in a dose-dependent manner. The highest effective dose was 5 µg/eye. Considering the vitreous volume difference between human and mouse (~1000:1 ratio), a range of 0.5 to 5 mg/eye is considered a logical effective dose level for humans.

In Phase I/II clinical study (Protocol 36-001), four dose levels of DE-122 (0.5 mg, 1.0 mg, 2.0 mg and 4.0 mg) were tested in subjects with refractory wet AMD. No dose-dependent events were reported and no new safety concerns were identified at all investigated doses. Most common AE was Subconjunctival haemorrhage (3 subjects, 25%) and all were considered to be due to the injection procedure.

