16.3. Study Populations

The following study populations are defined for analysis: Intention-to-treat (ITT) and Safety.

ITT Population: The ITT population will include all randomized subjects in the study.

Safety Population: The Safety population will include all randomized subjects who received at least one study medication. It will be the study population for safety analyses.

PK Population: The PK population will include all subjects who received at least one DE-122 and have at least one post-injection PK assessment. It will be the study population for PK analyses performed with subjects as treated.

Full Analysis Set: The Full Analysis Set (FAS) will include all randomized subjects who received at least one study medication and provided at least one post-baseline BCVA measurement. The efficacy analysis will be performed on the FAS or a subset of the FAS.

Per-Protocol Set: The Per-Protocol Set (PPS) Population is a subset of the FAS. It includes all FAS subjects without major protocol violations that could affect the primary efficacy endpoint.

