## **2. STUDY OBJECTIVES AND ENDPOINTS**

### **2.1. Objectives**

The primary objective is:

- To assess the safety and efficacy of repeated intravitreal injections of DE-122 (2.0 mg per eye and 4.0 mg per eye) given in combination with Lucentis® in subjects with wet age-related macular degeneration (AMD) compared with Lucentis® alone.

The secondary objectives are

- To evaluate the pharmacokinetics and immunogenicity of DE-122 following repeated IVT injections of DE-122 in subjects with wet AMD in serum samples.
- To evaluate biomarker candidates of DE-122 following repeated IVT injections of DE-122 in subjects with wet AMD in both serum and aqueous humor samples.

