## 10. PHARMACOKINETIC ANALYSES

All PK analyses will be performed on the PK population, with subjects as treated. Pharmacokinetic parameters (AUC,  $C_{max}$ ,  $t_{max}$ , and  $t_{1/2}$ ) will be summarized descriptively by actual treatment arm and analysis interval.

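### The SAP limits the PK population to subjects with a quantifiable level, which the protocol does not require; any subject entirely below the limit is dropped, and mean Cmax is then biased upward

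*SAP*

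**What the plan says.** **Protocol, section 16.3.** The PK population is everyone who "received at least one DE-122 and have at least one post-injection PK assessment". There is no condition on the assay result.

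**SAP, section 5.5.** The subject must "have at least one quantifiable post-injection PK serum assessment". The SAP states that it applies to Protocol Amendment 07. It explains the removal of the interim analysis (section 6.6) but does not mention this change.

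**SAP, section 10.** "All PK analyses will be performed on the PK population, with subjects as treated". No other set is used. Parameters are estimated separately for Day 1 to Week 4 and for Week 20 to Week 24 (section 4.4.2).

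**Values below quantification.** Protocol section 13.2 names an ELISA but gives no limit. SAP section 6.3 has special-value rules for BCVA, SD-OCT and FA, and M-CHARTS, and none for concentrations.

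**Who is sampled.** Only subjects who consented before protocol Version 4.0 (protocol section 23.4.17). Their number is not given.

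**Role of PK.** It is a secondary objective: "To evaluate the pharmacokinetics and immunogenicity of DE-122 following repeated IVT injections of DE-122 in subjects with wet AMD in serum samples". Protocol section 7.1.1 says that systemic exposure "is anticipated to be significantly lower than the systemic exposure in over 500 cancer" subjects, most of them dosed intravenously, and concludes: "Therefore, no concerns regarding systemic toxicity are anticipated in this study".

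**The concern.** Membership of the analysis set depends on the variable being analysed. A subject who was dosed and sampled and never showed measurable drug is evidence on systemic exposure, but the SAP removes that subject from every PK summary. Mean Cmax then describes subjects with detectable drug, and the summary does not show how many had none.

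The disposition table (SAP section 7.1) does not recover that number. It reports how many subjects are in the PK population by arm. Since sampling stopped for those who consented under Version 4.0, a subject outside the set may never have been sampled, or may have been sampled and always below the limit.

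Two results are at stake: the level of exposure reported for a secondary objective, and the comparison of the two doses. The second is affected if the below-limit share differs by arm, because the arms are then averaged over differently selected subjects.

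**Working it through.** The plan states no figure to reproduce.

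**1. The two definitions.** Both require at least one DE-122 dose and at least one post-injection PK assessment. The SAP adds that the assessment be quantifiable. The SAP set is therefore a subset of the protocol set, and the difference is exactly the subjects whose post-injection samples are all below the limit. Protocol section 23.4.17 lists ten draws, one of them before the first injection, so exclusion requires up to nine results to be below the limit.

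**2. Inputs.** From the documents: 31 and 28 subjects planned in the two DE-122 arms, an upper bound on those sampled. Not in the documents, and so assumed: the share q of sampled subjects who are entirely below the limit, the distribution of Cmax, and its coefficient of variation (CV). For simplicity each subject has one Cmax and is dropped when it falls below the limit.

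**3. Inflation relative to zero-coding.** If dropped subjects would otherwise count as 0, the mean is multiplied by 1/(1 − q).

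- q = 0: 1.00
- q = 10%: 1/0.90 = 1.11
- q = 25%: 1/0.75 = 1.33
- q = 50%: 1/0.50 = 2.00

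**4. Inflation relative to the true mean.** A below-limit level is low, not zero. With lognormal Cmax and log-scale SD σ = √ln(1 + CV²), the mean among quantifiable subjects divided by the true mean is Φ(σ − z_q)/(1 − q), where z_q is the standard normal quantile of q.

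| q | CV 30% | CV 50% | CV 100% |
|---|---|---|---|
| 10% | 1.05 | 1.07 | 1.09 |
| 25% | 1.11 | 1.17 | 1.25 |
| 50% | 1.23 | 1.36 | 1.59 |

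The inflation is thus about 5–9%, 11–25% and 23–60%. Relative to substituting half the limit, over the same CVs, it is 1.07–1.10 at q = 10% and 1.44–1.64 at q = 50%.

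**5. Dose comparison (illustration only).** Assume 50% below the limit at 2.0 mg, 10% at 4.0 mg, a common limit set to 1, a common σ and a true ratio of means of 2.

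- σ = ln 2 / 1.2816 = 0.541, a CV of 58%.
- True means: exp(σ²/2) = 1.158 at 2.0 mg and 2 × 1.158 = 2.315 at 4.0 mg.
- Means among quantifiable subjects: 1.158 × 0.7057/0.50 = 1.634 and 2.315 × 0.9658/0.90 = 2.484, inflated by 1.41 and 1.07.
- Ratio under the SAP rule: 2.484/1.634 = 1.52.
- Everyone kept, below-limit coded 0: (0.90 × 2.484)/(0.50 × 1.634) = 2.236/0.817 = 2.74.
- Everyone kept, below-limit coded at half the limit: (2.236 + 0.10 × 0.5)/(0.817 + 0.50 × 0.5) = 2.286/1.067 = 2.14.

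In this case the SAP rule shrinks the ratio, zero-coding overstates it by more, and half the limit comes closest to 2.

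**6. Other parameters.** A subject with no quantifiable level has no estimable half-life or tmax under either definition and, on the ordinary reading, no estimable AUC. The choice of population therefore changes Cmax, the counts and the denominator, but not a summary of the other three given only where estimable.

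**The case against.** **The premise is not established.** The protocol's statement on exposure is relative, against cancer subjects mostly given 10 mg/kg weekly by intravenous infusion. It does not predict levels below the assay limit, and exclusion needs every post-injection sample, including those at 3 and 48 hours, to be below it. This stands: the bias is conditional and may be zero. Nor do the documents show that fewer subjects at 2.0 mg will be quantifiable; that is only possible.

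**The direction is conservative.** Overstating mean exposure works against a claim of low exposure, so a reader should not infer false reassurance about systemic safety. This also stands for the mean. It does not cover the dose comparison, where unequal exclusion can move the ratio.

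**A larger distortion is tempting.** One might multiply a two-fold ratio by (1/0.9)/(1/0.5) and conclude that it would be reported as 1.1. That takes below-limit levels to be truly zero, which nothing in the documents supports; the lognormal model with the same shares gives about 1.5. One might also infer that AUC is inflated, but where AUC is reported only when estimable, restoring the population leaves it essentially unchanged.

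**The information is partly available, and the stakes are limited.** The size of the PK population is reported by arm and data listings are planned, so individual values can be inspected. PK summaries are descriptive, no hypothesis is tested, and the protocol leaves analysis detail to the SAP. This lowers the urgency. It does not resolve the conflict: the protocol defines this population itself, and no planned table separates subjects never sampled from those always below the limit.

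**Conclusion.** The concern holds as a conditional one. It is certain that the two definitions differ, that the SAP does not explain the difference, and that the SAP's rule selects on the outcome with no stated handling of below-limit values. Even a subject kept in through one Week 20 value has no rule for a Day 1 to Week 4 profile that is entirely below the limit.

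If any sampled DE-122 subject is entirely below the limit, mean Cmax is biased upward, and the dose comparison may be distorted. The size cannot be fixed from the documents. The figures above rest on assumed values of q and, apart from the zero-coding factor, on a lognormal Cmax; the 1.5 dose ratio is one illustration and not a forecast. If every sampled subject has a quantifiable level, there is no bias and only the inconsistency remains.

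This should be corrected, because PK is a secondary objective and the remedy is cheap. It does not affect the primary endpoint.

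**What to change.** - Restore the PK population of protocol section 16.3 in SAP section 5.5.
- Report, by arm and time point, the number and percentage of sampled subjects and of samples below the limit, separately from subjects never sampled. State the limit.
- Add a below-limit rule to SAP section 6.3. Summarise Cmax with below-limit profiles included under one convention fixed in advance: half the limit, or a median or censored-data summary, rather than zero alone.
- Report AUC, tmax and half-life only where estimable, with n for each parameter and interval.
- If the quantifiable condition is kept, document it in the SAP as a departure from the protocol, with the reason.

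The cost is SAP wording and minor programming. No new data are needed.

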### **5.6. Biomarker Population**

The *Biomarker Population* will include all subjects who receive at least one DE-122 and have at least one quantifiable post-injection biomarker serum assessment. It will be the study population for biomarker analyses.

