6. OBJECTIVES

Primary Objective:

- To assess the safety and efficacy of repeated IVT injections of DE-122 (2.0 mg/eye and 4.0 mg/eye) given in combination with Lucentis® in subjects with wet AMD compared with Lucentis® alone.

Secondary Objective:

- To evaluate the pharmacokinetics and immunogenicity of DE-122 following repeated IVT injections of DE-122 in subjects with wet AMD in serum samples.
- To evaluate biomarker candidates of DE-122 following repeated IVT injections of DE-122 in subjects with wet AMD in both serum and aqueous humor samples.

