16.5. Demographics and Baseline Characteristics

Age, sex, race, ethnicity, and baseline assessments will be summarized descriptively by treatment arms.

Subjects with abnormal medical history will be tabulated by treatment arm and body system.

Subjects using any prior medications will be tabulated by treatment arms, Anatomical Therapeutic Chemical levelbrys, and preferred term specified in the World Health Organization Drug Dictionary Enhanced ([World Health Organization Drug Dictionary, 2011](#)).

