16.10. Other Analysis

16.10.1. Biomarker Analysis

To explore the biomarkers, serum and aqueous humor samples will be collected at specified time points and measured for levels of angiogenesis-related proteins. Changes from baseline in levels of biomarkers will be summarized descriptively by treatment arms.

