#### **2.2.6. Biomarker Endpoint**

For biomarker investigation, serum samples and aqueous humor samples from the study eye will be measured for levels of angiogenesis-related proteins.

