## 12. BIOMARKER ANALYSIS

Translational Research will provide the report of biomarker investigation. Scores, changes from baseline and percent change from baseline in levels of potential biomarkers will be summarized descriptively by actual treatment received and analysis visit. Besides the summary tables, plots of biomarker measures versus analysis visit will be provided. Pearson's correlation between change from baseline in BCVA and each biomarker will be analyzed by actual treatment and analysis visit. The 95% confidence interval of the correlation coefficient based on Fisher's Z transformation will be provided.

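### The Biomarker Population in SAP 5.6 requires a DE-122 injection, so the whole Sham + Lucentis arm (17 of 76) is left out of the planned biomarker summaries

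*SAP*

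**What the plan says.** SAP 5.6 defines the Biomarker Population as "all subjects who receive at least one DE-122 and have at least one quantifiable post-injection biomarker serum assessment" and makes it the set for biomarker analyses. SAP 5.5, directly above, defines the PK Population as "all subjects who receive at least one DE-122 and have at least one quantifiable post-injection PK serum assessment". The two conditions differ only in the kind of assessment named.

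SAP 12 plans summaries, plots and correlations of the biomarkers. For the correlations it says "correlation between change from baseline in BCVA and each biomarker will be analyzed by actual treatment and analysis visit". It names no population of its own, so SAP 5.6 governs.

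Protocol 16.10.1 says "Changes from baseline in levels of biomarkers will be summarized descriptively by treatment arms". Protocol 16.3 defines no Biomarker Population. The only set there that depends on DE-122 is the PK set: "The PK population will include all subjects who received at least one DE-122 and have at least one post-injection PK assessment".

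The secondary objective (protocol 6, repeated in SAP 2.1) reads "To evaluate biomarker candidates of DE-122 following repeated IVT injections of DE-122 in subjects with wet AMD in both serum and aqueous humor samples". The endpoint in SAP 2.2.6 is that "serum samples and aqueous humor samples from the study eye will be measured for levels of angiogenesis-related proteins".

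**The concern.** For PK the DE-122 condition is natural, because a subject who never received the antibody has no concentration of it to describe. That reason does not carry over to angiogenesis-related proteins, which can be measured in any subject. In SAP 5.6 the condition serves only to remove the control arm, and the near-identical wording suggests it was carried over from SAP 5.5.

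The control arm matters here because protocol 10.1.2 gives Lucentis to all groups. A change from baseline in Arm 2 or Arm 3 therefore reflects Lucentis plus DE-122, and only Arm 1 shows what happens on Lucentis alone. Without it, a reader of the SAP 12 outputs cannot tell whether a change in a protein accompanies DE-122 or would have occurred anyway. The same holds for the correlations with BCVA.

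Arm 1 subjects are still scheduled for sampling: up to about 10 biomarker blood draws, about 100 mL in total (protocol 23.4.20), and optional aqueous humor samples that are also written for Sham visits (protocol 7.5.2.4 and 7.5.2.8). As the SAP stands, none of these data enters a planned biomarker summary.

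**Working it through.** **Inputs.** Arm sizes of 17, 31 and 28, total 76 (protocol 16.2.1, SAP 3.3). Allocation of the first 6 subjects 1:1 to Arms 1 and 2, then about 70 subjects 1:2:2 (protocol 16.2.3). Arm 1 treatment of Sham plus Lucentis 0.5 mg (protocol 7.1); Sham does not enter the eye (protocol 9.4).

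**Reproducing the planned arm sizes.**
- Stage 1: 6 × 1/2 = 3 in each of Arms 1 and 2.
- Stage 2: 70 × 1/5 = 14 in Arm 1, and 70 × 2/5 = 28 in each of Arms 2 and 3.
- Totals: 3 + 14 = 17, 3 + 28 = 31, 0 + 28 = 28; sum 76. This matches the plan exactly.

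**Applying the SAP 5.6 condition, with subjects treated as assigned.**

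| | Arm 1 | Arm 2 | Arm 3 | Total |
|---|---|---|---|---|
| Planned | 17 | 31 | 28 | 76 |
| Can meet the DE-122 condition | 0 | 31 | 28 | 59 |
| Excluded by it | 17 | 0 | 0 | 17 |

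- Largest possible population: 59/76 = 77.6%.
- Excluded: 17/76 = 22.4% of the trial and 17/17 = 100% of Arm 1.
- With a condition that either DE-122 or Lucentis satisfies, up to 76 subjects (17/31/28) could enter.

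The requirement for a quantifiable serum value can reduce these counts further, so 59 and 76 are upper limits. An Arm 1 subject given DE-122 by mistake would enter the population, but SAP 12 reports by actual treatment, so the Sham + Lucentis group would still be empty. The disposition table in SAP 7.1 counts the Biomarker Population by treatment arm and would show 0 for Arm 1.

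**Comparing the texts.** Protocol 16.10.1 speaks of treatment arms without qualification. Protocol 16.5 uses the same phrase for demographic and baseline data ("baseline assessments will be summarized descriptively by treatment arms"), where all three arms are plainly meant. Where the protocol wants a DE-122 condition, for PK in 16.3, it states one. For biomarkers the restriction appears only in SAP 5.6, without explanation.

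**The case against.** The best counter-argument is that reporting by arm need not mean reporting all three arms. SAP 10 summarizes PK by actual treatment arm in a population that excludes Arm 1 by definition, protocol 16.10.1 names no population, and protocol 16.2 leaves analysis details to the SAP. The secondary objective is worded around DE-122 and, unlike the primary objective, mentions no comparison with Lucentis alone. A DE-122-only set could therefore have been intended. This part stands: intent cannot be settled from the text. But neither document states that intent, and protocol 16.3 shows that the authors wrote a DE-122 condition when they wanted one. Identifying a biomarker of DE-122 in patients who all receive Lucentis also calls for the Lucentis-alone group.

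It can also be said that little is lost. The work is exploratory and descriptive, no hypothesis is defined (protocol 16.2.2), and SAP 12 plans no between-arm difference of the kind SAP 8.1.1 gives for BCVA. Protocol 16.2 says that all study parameters will be listed, so any Arm 1 values should survive in listings and could be tabulated later. SAP 12 also mentions a separate Translational Research report, which may cover Arm 1. These points limit the severity. They do not repair the definition: an empty control group defeats a side-by-side description, and the content of that report is unknown.

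Finally, 17 is the planned size of Arm 1, not the number with usable biomarker data. Aqueous humor sampling is optional, and the 48-hour serum samples apply only to subjects who consented before protocol Version 4.0. The number of Arm 1 subjects with data could be well below 17.

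**Conclusion.** The concern holds. Followed literally, SAP 5.6 leaves one of the three treatment groups empty in every biomarker summary, plot and correlation under SAP 12. This does not fit the unrestricted plan in protocol 16.10.1 and removes the only concurrent Lucentis-alone reference. The population is capped at 59 of 76 planned subjects, and the 17 lost are the entire control arm. The count assumes the planned arm sizes and treatment as assigned; whether the exclusion was deliberate remains open.

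This should be fixed, but the effect is confined to a descriptive secondary objective. No formal contrast is lost, and randomization, dosing, primary efficacy and safety are unaffected.

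**What to change.** In SAP 5.6, replace the DE-122 condition with receipt of one or more injections of either DE-122 or Lucentis, following the Full Analysis Set in SAP 5.3. Keep the requirement for a quantifiable post-injection value, and keep the reporting by actual treatment in SAP 12, now with all three groups.

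In the same edit, apply the quantifiable-value requirement to the matrix being analyzed. SAP 5.6 asks for a serum value even though aqueous humor is also part of the endpoint. This is a secondary point, and the main one does not depend on it.

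If a DE-122-only analysis is what the sponsor wants, SAP 5.6 and SAP 12 should say so, give the reason, and record it as a departure from protocol 16.10.1.

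The cost is SAP wording and slightly more tabulation. Arm 1 samples are already scheduled; assaying them would be an added expense only if it was not already planned.
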